### 5.8 Clinical Examiner Qualifications

Clinical examiner(s) involved in the screening, safety and efficacy assessments will be appropriately qualified dental professionals, registered to practice in the USA.

Oral examinations to determine subject eligibility and to monitor the safety/performance of study products will be performed by appropriately trained clinical examiner(s), with prior relevant clinical experience. Clinical examiner(s) will also be experienced in use of the VITA Bleachedguide (or equivalent) for measurement of tooth color, the MLSI (or similar) for measurement of dental stain and the evaporative (air) stimulus measured by Schiff sensitivity score for determination of DH status.

## 6 INVESTIGATIONAL/STUDY PRODUCTS

For the purposes of this study, per International Conference on Harmonization (ICH) guidelines, and Haleon policy, study intervention is defined as any investigational intervention(s), marketed

Property of Haleon- Confidential

May not be used, divulged, published or otherwise disclosed without the consent of Haleon

product(s), placebo, or medical device(s) intended to be administered to a study participant according to the study protocol.

This includes a product with a marketing authorization when used or assembled (formulated or packaged) in a way different from the approved form, or when used for an unapproved indication, or when used to gain further information about an approved use.

## 6.1 Investigational/Study Product Supplies

The following study products will be supplied by the Clinical Supplies Department, Haleon:

**Table 6-1 Investigational/Study Product Supplies**

	Test Dentifrice	Reference Dentifrice
Product Description	Dentifrice containing 5% w/w KNO 3 , 1% alumina, 5% STP and 1150ppm fluoride as sodium fluoride	Dentifrice containing 1150ppm fluoride as sodium fluoride
Product Name	Experimental Dentifrice	Aquafresh Cavity Protection
Product Master Formulation Code	CCI [REDACTED]	Commercial product – US marketplace (CCI [REDACTED])
Pack Design	Carton of overwrapped tubes	Carton of overwrapped tubes
Dispensing Details	Dentifrice kit dispensed at Screening Visit	Dentifrice kit dispensed at Screening Visit
Return Requirements	All used/unused samples to be returned	All used/unused samples to be returned
Dose/Application	Subjects will dose the toothbrush provided with a strip of dentifrice (a full brush head) on each brushing occasion. Subjects will brush for two timed minutes twice daily (morning and evening); subjects will be permitted to rinse with water post-brushing.	
Route of Administration	Oral topical	

The following sundry items will be supplied by the sponsor's Global Clinical Supplies Group.

**Table 6-2 Sundry Items**

Sundry Items to be supplied:

Item	Supplied By	Pack Design	Dispensing Details	Return/Disposal Details	
				Used Samples	Unused Samples
parodontax Complete Protection Soft-Bristled Toothbrush (US market)	Haleon	Twin Pack	Two packs at Screening (visit 1) Subjects will be instructed by site staff to start using a new brush at V3 and at V4.	Destroy at site using site disposal procedures	Return
Countdown Timer	Haleon	Individual commercial pack	At Screening (visit 1)	To be kept by subject or disposed of.	Return
Opalescence Go 15% Peroxide Kit [USA Marketplace]	Study Site	Commercial pack	First use at site, dispensed for at-home use at visit 2	Return	Return
Petroleum Jelly	Haleon	Commercial pack	First use at site, dispensed for at-home use at visit 2	Destroy at site using site disposal procedures	Return
Dental Floss	Haleon	Commercial pack	First use at site, dispensed for at-home use at Visit 2	Destroy at site using site disposal procedures	Return

Detailed instructions for the return of study product/study supplies for the accountability checks and subsequent destruction which will be provided by Haleon during the study in time for study close out visit.

The toothbrushes are marketed medical devices and will be used in accordance with the label instructions.

**6.1.1.1 Application of the Peroxide Bleaching**

The peroxide tooth bleaching procedure should be performed at-home (except for the first application which will be performed under supervision at the study site) following manufacturer instructions. Subjects should brush their teeth with the study dentifrice and floss their teeth prior to applying the peroxide gel. Subjects will apply the supplied gel-containing tray to their maxillary teeth per the product instructions. Subjects should apply their peroxide-containing

Property of Haleon- Confidential

May not be used, divulged, published or otherwise disclosed without the consent of Haleon

tray to their maxillary teeth once per day for 15 timed minutes immediately after either their morning or evening tooth brushing with their assigned study dentifrice. Subjects should attempt to perform the tooth bleaching at approximately the same time of day wherever possible. Subjects should perform peroxide bleaching for 7 consecutive days. Should subjects experience gum sensitivity/irritation due to the peroxide, they should apply a thin layer of the supplied petroleum jelly to the affected gum tissue prior to applying the peroxide, taking care not to contact the teeth with the petroleum jelly.

Subjects should note every bleaching event in their diaries to help monitor compliance.

### 6.1.2 Medical Devices

The definitions and procedures detailed are in accordance with ISO 14155.

- The Haleon manufactured medical devices (provided for use in this study) are the study toothbrushes.
- All device deficiencies (including malfunction, use error and inadequate labelling) shall be documented and reported by the investigator throughout the clinical investigation (see Section 10.10) and appropriately managed by the sponsor.

### 6.1.3 Dosage Form and Packaging

The study products are dentifrices, intended for topical oral use, and will be applied by toothbrushing using a manual toothbrush.

The experimental dentifrice will be manufactured and filled into plain white tubes by the sponsor; the reference dentifrice will be supplied in its commercial pack and sourced from the market the study is performed in (USA). All study dentifrices will be overwrapped in white vinyl (to mask their identity and obscure the branding of the marketed product) with a study label affixed. The content of the product labels will be in accordance with all applicable regulatory requirements and will be the responsibility of the sponsor's Global Clinical Supplies Group. Each study label will contain, but not be limited to, protocol number, directions for use and storage requirements.

Each subject will receive sufficient tubes of their assigned study dentifrice for usage during the 24-week treatment period. Sundry items (including the peroxide bleaching treatment) will be supplied in their commercial packaging for dispensing by study staff as specified in [Table 6.2](#).

Care should be taken with the supplied products and their labels so that they are maintained in good condition. It is important that all labels remain intact and legible for the duration of the study. Subjects should be instructed to not remove or deface any part of the study label.

All products supplied are for use only in this clinical study and should not be used for any other purpose.

### 6.1.4 Preparation and Dispensing

Subjects will be assigned to study treatment in accordance with the randomization schedule generated by an approved sponsor vendor, prior to the start of the study, using validated software.

The product dispensing area will be separate from the clinical examination area. Study dentifrices and peroxide bleaching treatment will be dispensed to the subject, by trained site personnel. These staff members will not be involved in any safety/product performance assessments or any other aspect of the study that could be influenced by the knowledge of

Property of Haleon- Confidential

May not be used, divulged, published or otherwise disclosed without the consent of Haleon

product a subject has been assigned to. An additional member of the site staff will verify the dispensing procedure has been completed accurately for each subject.

## 6.2 Administration

Only subjects enrolled in the study may receive study products and only authorized site staff may supply or administer study products. All study interventions must be stored in a secure, environmentally controlled, and monitored (manual or automated) area in accordance with the labeled storage conditions with access limited to the authorized site staff only.

Subjects will be instructed to self-administer their assigned study dentifrice and tooth bleaching treatment according to the usage instructions provided to the subject. Additionally, subjects will undergo supervised brushing with dentifrice at Visit 1 and 2 and application of the tooth bleaching treatment at Visit 2 to ensure compliance with application instructions. The reference dentifrice and the tooth bleaching treatment are commercially available, and the application instructions described in this protocol are consistent with their label instructions. The experimental dentifrice is intended for commercialization and the application instructions here are consistent with the intended label instructions.

To help ensure subjects understand the amount of dentifrice they should use each time they brush, brushing instructions and diary completion requirements:

- Staff will demonstrate dispensing a full ribbon of dentifrice along the length of the toothbrush head to each randomized subject and supervise their first brushing with study dentifrice (Visit 1&2) and diary completion at the screening visit (Visit 1).
- Staff will demonstrate and aid subjects for their first application of the peroxide tooth bleaching procedure at Visit 2.
- staff will review diary completion and subject's study products at Visits 2-5.

On-site administration of study products will also be recorded in the CRF.

Instructions on usage of the study products are detailed in the Appendices.

### 6.2.1 Product Usage Errors

In this study, product usage errors may result, in this study, from the administration or consumption of:

- the wrong product,
- by the wrong subject,
- at the wrong time,
- or at the wrong dosage.

Such errors occurring to a study subject are to be captured in the CRF. In the event of a product usage error, the sponsor should be notified **immediately and under no circumstance should this exceed 24 hours.**

Product usage errors are reportable irrespective of the presence of an associated AE, including:

- Usage errors involving subject exposure to any of the study products;
- Potential product errors or uses outside of what is foreseen in the protocol that do or do not involve the participating subject.

If a study product usage error is accompanied by an AE, as determined by the investigator, the usage error and, any associated adverse event(s) are to be captured in the CRF AE form.

Property of Haleon- Confidential

May not be used, divulged, published or otherwise disclosed without the consent of Haleon

### **6.2.2 Overdose**

An overdose is a deliberate or inadvertent administration of a product at an amount higher than specified in the protocol.

Overdose is not likely to occur in this study.

Overdose per se is not an AE. However, any clinical sequelae of an overdose should be reported as an AE (and serious adverse event (SAE), if appropriate). For reporting, follow the AE and SAE reporting instructions.

### **6.3 Investigational/Study Product Storage**

The investigator or designee must confirm appropriate temperature conditions have been maintained during transit for all study products received and any discrepancies are reported and resolved before use according to the supplied shipping documentation.

The investigator, or designee, will ensure that all study products are stored in a secured area with controlled access under required storage conditions and in accordance with applicable regulatory requirements and the product label.

Site systems must be capable of measuring and documenting (for example, via a log), at a minimum, daily minimum and maximum temperatures for all site storage locations (as applicable, including frozen, refrigerated, and/or room-temperature products). This should be captured from the time of first product receipt throughout the study. Even for continuous monitoring systems, a log or site procedure that ensures active daily evaluation for excursions should be available. The operation of the temperature-monitoring device and storage unit (for example, refrigerator), as applicable, should be regularly inspected to ensure it is maintained in working order.

Any excursions from the product-label storage conditions should be reported to appropriate site staff upon discovery and communicated to sponsor as soon as possible. The site should actively pursue options for returning the product to the storage conditions as described in the labeling, as soon as possible. Excursions from the storage requirements, including any actions taken, must be documented as a protocol deviation and reported to the Sponsor.

Once an excursion is identified, the affected product (or products) must be quarantined and not used until the sponsor provides documentation of permission to use. Use of any of the affected product(s) prior to sponsor approval will be considered a protocol deviation.

Site staff will instruct subjects on the proper storage requirements for all take-home products.

### **6.4 Investigational/Study Product Accountability**

All products supplied are for use only in this clinical study and should not be used for any other purpose.

All study products must be received by a designated person at the study sites, handled and stored safely and properly, and kept in a secured location to which only the staff have access. Upon receipt, all study products should be stored according to the instructions specified on the product labels. Study products are to be dispensed only to subjects enrolled in the study in accordance with the protocol, by authorized site staff.

The investigative site must maintain adequate records documenting the receipt, use, loss, or other disposition of all the product supplies. All study products will be accounted for using the

investigational/study product accountability form/record. The investigator is responsible for study product accountability, reconciliation, and record maintenance.

The accountability records must be available for inspection by the study monitor during the study. Monitoring of product accountability will be performed by the monitor during site visits and at the completion of the study.

Subjects should return their used and unused study products to the clinical site at Visit 5 in accordance with the study schedule. Study product return will be documented. Subjects will complete diaries to detail their usage of study products which will be used to monitor usage compliance.

#### **6.4.1 Destruction of Investigational/Study Product Supplies**

At the end of the study, the Principal Investigator or an appropriate designee, and a representative of Haleon (study monitor) will inventory all used and unused study products and sundry items. The investigational/study product accountability record for returned study products will then be completed. All study product (used and unused) for this clinical study (including empty containers), will be returned for destruction to the Haleon Clinical Supplies Department or designated vendor using the return instructions provided. Detailed instructions for the return of study product/study supplies for the accountability checks and subsequent destruction will be provided by Haleon during the study in time for study close out visit.

#### **6.5 Blinding and Allocation/Randomization**

All subjects will be centrally randomized to one of the two study products using an Interactive Response Technology (IRT). Before the study is initiated, training, login information and directions for the IRT will be provided. Study products will be dispensed according to the instruction received through the IRT at the appropriate study visits.

Returned study products should not be re-dispensed to any subject.

The investigator's knowledge of the product allocation should not influence the decision to enroll a subject or affect the order in which subjects are enrolled.

This study is described as single-blind (the clinical examiner(s) performing the efficacy assessments will be blinded to the product received). To ensure the examiner(s) remains blinded throughout the study, the examiner(s) will not be permitted in any area where study product is stored, dispensed, or in use staff involved in the preparation and dispensing of study products will work in a separate area, and subjects will be instructed not to remove study products from the opaque bags provided/cartons outside of the dispensing room, while at the study site. Dispensing staff will not be involved in any efficacy/safety assessment procedures during the study.

Site staff, study statistician(s), data management staff and other employees of the sponsor and vendors acting on behalf of the sponsor, who may influence study outcomes will be blinded to the product allocation.

Prior to randomization, subjects will be stratified on their DH status as detailed in [Section 5.4](#).

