The subjects in this study who have self-reported DH will be clinically evaluated to confirm their DH status. Whilst there are no protocol requirements associated with this assessment, DH is prevalent at 30-50% of the population ([West, 2023b](#)) and the enrollment to this study is expected to mirror this. It is anticipated that the test dentifrice, will be marketed for consumers with DH. However, it is anticipated that it will be purchased both by consumers with DH and those without, but who are recommended to use an anti-sensitivity dentifrice prior to, during and post peroxide tooth bleaching. A mixed population of those with clinically-diagnosed DH and those without is therefore appropriate. Subjects will be stratified according to their clinically-diagnosed DH status [DH positive or negative] to ensure a balanced population across treatment groups.

Demography information will be recorded as part of this study, including age, race and gender. In accordance with the United States Food and Drug Administration (US FDA) guidelines ([FDA, 2005](#)) the ethnicity of subjects will also be captured.

According to the International Conference on Harmonisation (ICH) guidelines ([ICH, Nov 2016](#)), for a study to be classified as truly double-blind, not only does the examiner (and any appropriate member of staff who may be involved in the dispensing of products, analysis of data etc.) need to be blind to the treatment a subject receives, but the products under test must be identical in every way (color, flavor, appearance, packaging). Given the experimental dentifrices and the reference dentifrice will differ in appearance and flavor, the level of blindness for this study is described as 'examiner blind'. The study will be blinded with respect to the dental examiner(s) and other outcome assessors to ensure there is no bias in the assessments. Study dentifrices will be supplied in overwrapped tubes. The blind will be maintained by staff involved in dispensing, brushing instruction and supervised brushings who will not be involved in any clinical examinations.

Property of Haleon- Confidential

May not be used, divulged, published or otherwise disclosed without the consent of Haleon

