## 6.7 Compliance

To facilitate subject compliance with product usage requirements:

- First use of their assigned study dentifrice will be carried out under supervision at the study site at the end of the screening visit (Visit 1) and additionally at Visit 2; study staff will demonstrate the correct amount of dentifrice to dispense and how to use the timer to ensure a 2-minute brushing time. Subjects will be provided with a diary at Screening (Visit 1) to record each completed brushing.
- First use of the peroxide tooth bleaching procedure will be carried out under supervision at the study site at Visit 2; study staff will demonstrate the application of the bleaching gel according to manufacturer's instructions. Subjects will be provided with a diary to record each completed tooth bleaching treatment.
- Subjects will attend each study visit with all tubes of dentifrice provided (used and unused) for a visual check of product usage, and with their completed diary for review by study staff. Any suspected over or under use, the number of any missed or additional brushings will be documented as deviations in the CRF; subjects will be re-instructed in the correct use of product and diary completion, as required.
- Subjects will also use the diary to note any issues with their study product, any oral problems, illnesses and new medications/ treatments. Details relevant to safety or efficacy should be reviewed by the investigator (or suitably qualified designee) and transcribed to the CRF, as appropriate; AEs must be documented in the CRF.

The number of any missed or additional applications or doses will be captured as protocol deviations. Subjects will be re-instructed in the correct usage requirements and diary completion as needed.

A record of the number of dentifrice tubes dispensed to and taken by each subject must be maintained and reconciled with study intervention and compliance records. Intervention start and stop dates, including dates for intervention delays and/or dose reductions will also be recorded in the CRF.

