#### **8.2.1 Visit 2/ start of peroxide tooth bleaching**

Procedures will be conducted by the Investigator, or suitably qualified designee.

Subjects will undergo, in the following order (wherever possible).

1. Changes in concomitant medication or non-drug treatments/procedures will be documented.
2. Spontaneous reporting of AEs and those elicited by asking subjects to respond to a non-leading question such as “How do you feel?” will be assessed.
3. Subject will return study products and diary for visual inspection to evaluate product compliance and adherence to protocol.
4. Subject undergoes an OST examination.
5. Subject undergoes assessment of tooth color (Vita Shade) and extrinsic tooth stain (MLSI).
6. Subject continuance in the study is assessed. Subjects who do not meet the criteria for participation will be discontinued.
7. Subject completes the tooth sensitivity questionnaire.
8. Subject completes the whitening history questionnaire.
9. Subject undergoes supervised tooth brushing using their study dentifrice. Subject flosses their teeth.

Property of Haleon- Confidential

May not be used, divulged, published or otherwise disclosed without the consent of Haleon

10. Subject is dispensed the peroxide tooth bleaching kit (including petroleum jelly and dental floss) and instructions for at home use.
11. Subject undergoes the first application of the peroxide tooth bleaching under supervision at the study site.
12. AEs and incidents recorded.

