## 8.2.5 Study Procedures

### 8.2.5.1 Diary Review

The diary should be reviewed at every visit by the investigator, or suitably qualified designee, with the subject. Any subject comment captured in the diary which is considered an AE will be assessed and reported as defined in the [Adverse Event and Serious Adverse Events section](#) of this protocol.

Any additional comments relating to medications/treatments provided in the diary will be reviewed by the investigator or medically qualified designee with the subject and entered into the CRF as appropriate.

Additional and missed product applications will be considered deviations from the protocol and will be recorded on the Deviations Log and as a deviation in the CRF.

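### Protocol 6.5 keeps the shade examiner away from the product, but has no rule for the adverse-event question or the diary discussion that come before scoring at Visits 2–5

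*Protocol*

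**What the plan says.** **Level of blinding.** Protocol 6.5 calls the study single-blind: "the clinical examiner(s) performing the efficacy assessments will be blinded to the product received". Subjects are not blinded by design. Section 4.2 gives the reason: "Given the experimental dentifrices and the reference dentifrice will differ in appearance and flavor".

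**How the blind is kept.** The main rule in 6.5 is that "the examiner(s) will not be permitted in any area where study product is stored, dispensed, or in use". Around it stand overwrapped tubes (6.1.3), a separate dispensing area (6.1.4), an instruction to keep product bagged or boxed while on site (6.5), and dispensing and brushing staff who do no clinical examinations (4.2, 6.5). Sections 4.2 and 6.5 also say in general terms that outcome assessors, and site staff in a position to affect outcomes, are kept blind.

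**Visit procedures.** Sections 8.2.1 to 8.2.4 open each list with "Procedures will be conducted by the Investigator, or suitably qualified designee". At each of Visits 2–5 the adverse-event question is step 2. Step 3 reads "Subject will return study products and diary for visual inspection to evaluate product compliance and adherence to protocol". The soft-tissue examination is step 4, and shade and MLSI scoring is step 5.

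**Diary.** Section 8.2.5.1 says "The diary should be reviewed at every visit by the investigator, or suitably qualified designee, with the subject". Section 6.7 adds that "Subjects will also use the diary to note any issues with their study product".

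**Scoring.** Sections 9.2.1 and 9.2.2 give shade and MLSI to one trained examiner.

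**Investigator.** Section 6.5 also contains the sentence "The investigator's knowledge of the product allocation should not influence the decision to enroll a subject".

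**The concern.** Study success rests on one comparison of a visual score (Protocol section 3, SAP 1.2), so the examiner's blind is its main protection against assessment bias. The person most able to reveal the arm is the subject, who brushes with the paste twice a day. The listed safeguards deal with objects, rooms and dispensing staff. They do not deal with what a subject says when asked about adverse events, or has written in the diary.

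If the scorer also asks that question or goes through the diary, a remark on taste, color or sensitivity may be heard just before scoring. Section 4.2 plans for the same examiner(s) throughout, so something learnt at Visit 2 can still be known at Visit 5. Any resulting lean in the scores would be read as a product effect.

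**Working it through.** **1. Which contacts before scoring does a specific safeguard reach?**

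| Contact at Visits 2–5 | Position | Who may do it | Specific safeguard |
|---|---|---|---|
| Adverse-event question | step 2 | Investigator or designee (8.2.1–8.2.4, 10.4); dispensing staff are excluded from safety assessments (6.1.4, 6.5) | None |
| Check of tubes and diary completion | step 3 | Staff (6.2, 6.7), under the general visit header | Largely covered: product kept in bags or cartons, examiner barred from product areas |
| Diary review with the subject | every visit; placed before the examinations in the 4.1 narrative | Investigator or designee (8.2.5.1) | None |
| Shade and MLSI scoring | step 5 | One trained examiner (9.2.1, 9.2.2) | – |

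No passage says that the scorer must be someone other than the person who asks about adverse events or discusses the diary. No passage tells subjects not to describe their toothpaste to the scorer. The visit order applies only where possible, so it could be changed, but nothing asks for that.

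**2. The plan's own figures.** Inputs: difference 1, SD 2, 80% power, 20% dropout (Protocol 12.1); two-sided 5% (Protocol 12.3.1, SAP 4.4.1.2).

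- Normal approximation: n = 2 × (1.960 + 0.842)² × 2² / 1² = 62.8, so 63 per group.
- Exact t test: power 0.795 at 63 and 0.801 at 64 per group. The stated 64 is reproduced.
- Randomized total: 128 / (1 − 0.20) = 160, as stated.

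The point does not change these figures.

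**3. What a lean would do (illustration only).** Suppose there is no true difference and the scores favor the test paste by d shades on average. The documents give no value for d. A two-sample t test stands in for the planned repeated-measures model.

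- SE of the difference = 2 × √(2/64) = 0.354.
- Noncentrality = d / 0.354, with 126 degrees of freedom.

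| Assumed d | Noncentrality | Chance of p<0.05 |
|---|---|---|
| 0 | 0 | 5.0% |
| 0.1 | 0.28 | 5.9% |
| 0.25 | 0.71 | 10.8% |
| 0.5 | 1.41 | 28.9% |

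**4. How strong the lean would have to be.** d is an average over all subjects. If a fraction f in each arm reveals its arm, and the leans in the two arms add up to L shades in those subjects, then d = f × L. With f assumed to be 10%, d = 0.1 needs L = 0.1/0.10 = 1 shade, d = 0.25 needs 2.5 shades, and d = 0.5 needs 5 shades. The larger entries therefore need either frequent disclosure or a strong lean.

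**The case against.** The strongest reply is that the protocol already separates the roles in substance.

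- **The visit header is delegation wording.** At Visit 2 it also covers supervised brushing (step 9), which the examiner cannot attend under 4.2 and 6.5. The Visit 1 header likewise covers both scoring and dispensing. It cannot mean that one person does the whole list.
- **The routine check is assigned elsewhere.** Sections 6.2 and 6.7 give the tube and diary-completion check to staff, and 6.2 lists it beside the brushing supervision whose staff 4.2 bars from clinical examinations.
- **Disclosure is not automatic.** Tubes are overwrapped, each subject uses only one paste, and nothing says that subjects are told their allocation. A remark on taste identifies the arm only if the subject recognises the paste or the examiner knows how each one tastes. The subject's instruction sheet (15.2) asks about brushing, smoking, health and medication, not flavor.
- **The aim is stated.** Outcome assessors and influential site staff are to be blinded.

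Most of this stands, and it narrows the point to the adverse-event question and the 8.2.5.1 diary discussion. For these two contacts it does not close the gap. The general statements set an aim without a procedure, although 6.5 does set out procedures for the other routes. The dispensing staff, the group most clearly separated from the examiner, cannot take the adverse-event question. The repeat assessments (9.2.1.1) would not reveal a lost blind either: the same examiner rescores after 10 to 60 minutes, masked only to the first scores, so a consistent lean by arm could still give a high kappa.

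**Conclusion.** The gap is real but narrow. For two contacts that precede scoring at Visits 2–5, the protocol neither keeps the scorer out nor asks subjects to be discreet. The blind behind the primary endpoint could be lost this way. The percentages above depend wholly on the assumed lean and are not an estimate of bias in this trial. The point justifies a cheap clarification; it does not call the design into question.

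A reader might infer more, and the documents do not support it:

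- *That the protocol gives scoring, diary and adverse-event steps to one person.* It permits this but does not require it; the header has to be read with 6.2, 6.7 and 9.2.1.
- *That subjects know their allocation.* They can see and taste the paste. They are not said to be told which one it is.
- *That the false-positive rate is near 29%.* That figure needs an average lean of 0.5 shade, half the planned difference, and the documents give no sign of its size.
- *That 6.5 shows the investigator to be unblinded.* The sentence concerns enrollment decisions and order. It sits awkwardly beside the statement that influential site staff are blinded, and the two should be reconciled.

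**What to change.** Add to Protocol 6.5, after the rule on product areas:

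> Subjects are instructed not to discuss their toothpaste with the clinical examiner. The examiner who scores VITA shade and MLSI does not review the diary or returned product or conduct the adverse-event interview where another qualified designee is available; otherwise scoring is completed before these steps at each visit.

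Align the step order in 8.2.1–8.2.4 with this. Each list already ends with, or close to, a step for recording adverse events, so there is a natural place after scoring. At Visit 2 the moved steps should still precede the continuance decision. In 6.5, reconcile the sentence on the investigator's knowledge of the allocation with the statement that influential site staff are blinded.

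**Cost.** Protocol wording, a small change in visit flow and an entry in the delegation log. There is no new visit, assessment or sample-size change. The instruction to subjects should make clear that problems with the product are still to be reported.

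**Limits.** Separating the roles is the stronger protection, because reordering alone leaves what the examiner learnt at earlier visits. The documents do not establish that the site has another qualified person for the adverse-event interview, so full separation cannot be assumed to be free; hence the fallback. No restriction on the questionnaires is proposed, because at Visits 2 and 3 they follow scoring.
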